**Listing 16.2.9-3 Ophthalmic Examinations by treatment (FELLOW EYE)**

**Safety Set**

| Subject Number            | Visit     | Was OE Performed? | Date OE performed (YYYY-MM-DD) | FELLOW Eye assessed | IOP (mmHg) | Examination                        | Result        |
|---------------------------|-----------|-------------------|--------------------------------|---------------------|------------|------------------------------------|---------------|
| XXX-XX                    | Screening | Yes               | YYYY-MM-DD                     | Left eye            | XX         | Cornea                             | Normal        |
|                           |           |                   |                                |                     |            | Iris                               | Not done      |
|                           |           |                   |                                |                     |            | Vitreous                           | Abnormal      |
|                           |           |                   |                                |                     |            | Disc                               | Normal        |
|                           |           |                   |                                |                     |            | Retina other than AMD              | Abnormal      |
|                           | Lens      | Normal            |                                |                     |            |                                    |               |
|                           | Baseline  | Yes               | YYYY-MM-DD                     | Left eye            | XX         | Changes since previous assessment? | Yes: xxxxxxxx |
|                           |           |                   |                                |                     |            | Cornea                             | Normal        |
|                           |           |                   |                                |                     |            | Iris                               | Not done      |
|                           |           |                   |                                |                     |            | Vitreous                           | Abnormal      |
| Disc                      |           |                   |                                |                     |            | Normal                             |               |
| Retina other than AMD     | Abnormal  |                   |                                |                     |            |                                    |               |
| Lens                      | Normal    |                   |                                |                     |            |                                    |               |
| AREDS – Nuclear Sclerosis | <2        |                   |                                |                     |            |                                    |               |
| AREDS – Cortical          | >2        |                   |                                |                     |            |                                    |               |
| AREDS – PSC               | >2        |                   |                                |                     |            |                                    |               |
| Week n             | Yes       | YYYY-MM-DD        | Left eye                       | XX                  | .....      | .....                              |               |
| Week n             | Yes       | YYYY-MM-DD        | Left eye                       | XX                  | .....      | .....                              |               |
| .....                     |           |                   |                                |                     |            |                                    |               |
| XXX-XX                    | .....     |                   |                                |                     |            |                                    |               |
| .....                     |           |                   |                                |                     |            |                                    |               |

OE: Ophthalmic Examination, IOP: Intra Ocular Pressure

**Listing 16.2.9-4 Pregnancy test data by treatment**

**Safety Set**

| Subject Number   | Was pregnancy test done? | Type of sample taken | Date of sample (YYYY-MM-DD) | Result of Test |
|------------------|--------------------------|----------------------|-----------------------------|----------------|
| Intensive |                          |                      |                             |                |
| XXX-XX           | Yes                      | Urine sample         | YYYY-MM-DD                  | Negative       |
| XXX-XX           | Yes                      | Serum sample         | YYYY-MM-DD                  | Negative       |
| XXX-XX           | Yes                      | Urine sample         | YYYY-MM-DD                  | Negative       |
| XXX-XX           | Yes                      | Serum sample         | YYYY-MM-DD                  | Negative       |
| .....            |                          |                      |                             |                |
| Relaxed   |                          |                      |                             |                |
| XXX-XX           | Yes                      | Urine sample         | YYYY-MM-DD                  | Negative       |
| XXX-XX           | Yes                      | Serum sample         | YYYY-MM-DD                  | Negative       |
| XXX-XX           | Yes                      | Urine sample         | YYYY-MM-DD                  | Negative       |
| XXX-XX           | No                       | -                    | -                           | -              |
| .....            |                          |                      |                             |                |

\*Flags: H=High (Systolic - >180 and increase from baseline of >20, Diastolic - >105 and increase from baseline of >15)  
L=Low (Systolic - <90 and decrease from baseline of >20, Diastolic - <50 and decrease from baseline of >15)

**Section 16.2.10 – Listing of subject numbers who reported at least one safety event of special interest by event and treatment**

No output

**Section 16.2.11 – Case retrieval strategy listing**

No output

Table 2-1	Analysis set exclusion summary	8
Table 2.3-3	Study Assessment Windows	9
Table 2.7.2-1	Primary Efficacy Analyses.....	23
Table 2.7.2-2	Secondary Efficacy Analyses.....	23
Table 2.7.2-3	Exploratory Efficacy Analyses	23
Table 2.7.2.5-1	Mixed Models	26
Table 2.7.2.8-1	Logistic Regression Models.....	28

1 Introduction

[figure not shown]
Studies covered are listed in Table 1-1. The study design, objective, treatment duration, and efficacy variables for this indication may be different from other related studies due to different indications and phases of clinical development so that almost every study is unique. The main purpose is to provide project-level standards for the statistical analyses of efficacy and safety data which are common or similar across studies. This MAP can be used as a reference or guidance of statistical methods for future studies not listed in Table 1-1.

Table 1-1 Studies covered in the MAP

Indication /Study	Phase/ Duration	Treatment/ dose	Primary objective
AMD / RFB002	IV	(1) Intensive retinal fluid retreatment regimen (2) Relaxed retinal fluid retreatment regimen	To test the non-inferiority (visual acuity benefit that is not clinically worse) of intravitreal ranibizumab when administered to resolve IRF or SRF >200 µm under the fovea (relaxed retinal fluid management) relative to when administered to completely resolve both IRF and SRF (intensive retinal fluid management) in patients with wet AMD. The primary endpoint for the study will be the mean change in BCVA from baseline to month 24.

This is a randomised, multi-centre, non-inferiority trial investigating a relaxed fluid retreatment regimen relative to an intensive fluid retreatment regimen (using a non-inferiority margin of 5 letters on the primary endpoint of mean change in BCVA). After consenting to participate in the study, patients will participate in a screening period lasting up to 2 weeks to evaluate patient eligibility. After eligibility confirmation at the Baseline Visit, patients will be randomised in a 1:1 ratio to one of the two treatment arms i.e. intensive retinal fluid regimen or relaxed retinal fluid regimen within the appropriate stratum depending on the treatment at baseline for the non-study eye i.e. none, ranibizumab or other anti-VEGF therapy. Only one eye will be selected/treated as the study eye.

Patients withdrawn from the study prior to completion of the 24 month assessment visit will be asked to return for an Early Discontinuation evaluation 30 days +/- 7 days following their last study visit.

SCN = Screening, BSL = baseline, INITIAL 3 TR. = Initial 3 treatments at 4 weekly intervals both arms, Flexible interval Tr = treatment intervals will differ based on arm and disease activity, Pr. EP = Primary Endpoint, EOS= End of study.

Figure 1 Study design

2 Project standards

Treatment groups for the analysis

The group labels for the 2 treatment groups for the analysis are: “Intensive” (Group I) and “Relaxed” (Group II).

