**Table 14.2-2 Visual Acuity – Mixed Model Analysis**

Full Analysis Set

|                                    | Random Effects Mixed Model* |          |        |         | Treatment Effects |                   |
|------------------------------------|-----------------------------|----------|--------|---------|-------------------|-------------------|
|                                    | Num d.f.                    | Den d.f. | F-stat | p-value | Intensive (N=X)   | Relaxed (N=X)     |
| Baseline Effect                    | x                           | xx       | x.xx   | x.xxxx  |                   |                   |
| Treatment                          | x                           | xx       | x.xx   | x.xxxx  |                   |                   |
| Visit                              | x                           | xx       | x.xx   | x.xxxx  |                   |                   |
| Treatment*Visit             | x                           | xx       | x.xx   | x.xxxx  |                   |                   |
| Least Squares Means         |                             |          |        |         |                   |                   |
| Month 2 (95% CI)                   |                             |          |        |         | x.xx (x.xx, x.xx) | x.xx (x.xx, x.xx) |
| Month 12 (95% CI)                  |                             |          |        |         | x.xx (x.xx, x.xx) | x.xx (x.xx, x.xx) |
| Month 24 (95% CI)                  |                             |          |        |         | x.xx (x.xx, x.xx) | x.xx (x.xx, x.xx) |
| Treatment Effect            |                             |          |        |         |                   |                   |
| Month 2, Treatment Effect (95%CI)  |                             |          |        |         | x.xx (x.xx,x.xx)  |                   |
| Month 2, p-value                   |                             |          |        |         | x.xxxx            |                   |
| Month 12, Treatment Effect (95%CI) |                             |          |        |         | x.xx (x.xx,x.xx)  |                   |
| Month 12, p-value                  |                             |          |        |         | x.xxxx            |                   |
| Month 24, Treatment Effect (95%CI) |                             |          |        |         | x.xx (x.xx,x.xx)  |                   |

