2.3 Subgroup definitions

Sub-groups analyses may be included in exploratory and sensitivity analyses. Potential sub-groups:

- Randomisation Strata: Two treatment naïve eyes, one eye (first non-study eye) being treated with ranibizumab, and one eye (first non-study eye) being treated with an anti-VEGF other than ranibizumab.
- Age Group
- Sex
- Baseline BCVA group (≥ 70 letters, < 70 letters)
- Genotype sampling status
- Baseline lesion size
- Baseline IRF and/or SRF

Sub-group analyses may include descriptive analyses as well as forest plot(s) displaying treatment effects within each sub-group.

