2.8.2.2 Supportive/Sensitivity Analyses

The primary endpoint will be assessed using a mixed model as described above with no imputation for missing data. Sensitivity analyses may include re-fitting the model with missing data imputed using the LOCF and multiple imputation (as detailed further in Section 2.8.2.3).

In addition, the primary model will be fitted to the Per-Protocol Set as a supporting analysis. Secondary and exploratory models may also be fitted to the Per-Protocol set as supporting or sensitivity analyses.

Secondary endpoints will be assessed with no imputation for missing data. Sensitivity analyses may be conducted; including the re-fitting of models with missing data imputed using the LOCF and multiple imputation, if appropriate. Furthermore, the secondary endpoint models may be fitted to use the Per-Protocol Set as supporting analyses.

Statistical models with optional variables may be explored to identify which model(s) optimally fit the data. In addition, ANCOVAs may be used to confirm cross-sectional analyses, as applicable.

Furthermore, one of the secondary outcomes is to explore the percentage of patients with > 15 letter improvement. This analysis provides a further supporting analysis of the primary endpoint.

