2.8.2.3 Handling of missing values/discontinuations in efficacy analyses

For the primary analysis, there will be no imputation for missing data. The mixed model approach where all values recorded for each patient up to the time of withdrawal (or completion) are used is an appropriate model for data missing at random.

Sensitivity analyses will be conducted to explore the robustness of the data to the methods of dealing with missing data. These methods will include LOCF and multiple imputation.

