2.8.2.5 Mixed Modelling

The mixed models to be fitted are detailed in Table 2.8.2.5-1.

Table 2.8.2.5-1 Mixed Models

Model Number	Outcome Variable	Predictor/Covariate		Class Variable		Random Term
		Definite	Optional	Definite	Optional	
MM_1	Change in BCVA from baseline to 2, 12 and 24 months	
 • Treatment • Baseline BCVA • Visit (categorical) • Treatment by Visit Interaction 	
 • Stratification group • Cumulative weeks on treatment 	Treatment Visit Subject		Subject
MM_2	Change in BCVA from baseline to 2, 12 and 24 months	
 • Treatment • Baseline BCVA • Visit (categorical) • Treatment by Visit Interaction 	
 • Injection frequency • Cumulative number of weeks on treatment • Stratification group Baseline: 
 • Age • Lesion size • GA presence • Smoking status • Genotype saliva sample status • Baseline BCVA (<=70/>70) • Baseline IRF • IRF • Baseline SRF • SRF • PED • SRF resolved (y/n) 	Treatment Visit Subject	Stratum Centre	Subject
MM_3	Change in Geographic Atrophy from baseline to 2, 12 and 24 months.	
 • Treatment • Baseline GA area • Visit (categorical) • Treatment by Visit Interaction 	
 • Cumulative number of weeks on treatment Baseline: 
 • Age • BCVA • Injection frequency • Lesion size • GA presence • Smoking status • Genotype saliva sample status • Baseline BCVA (<=70/>70) • Baseline IRF • IRF • Baseline SRF • SRF • PED • SRF resolved (y/n) 	Treatment Visit Subject	Stratum Centre	Subject

Model Number	Outcome Variable	Predictor/Covariate		Class Variable		Random Term
		Definite	Optional	Definite	Optional	
MM_4	Change in CRT from baseline to 2, 12 and 24 months	
 • Treatment • Baseline CRT • Visit (categorical) • Treatment by Visit Interaction 	
 • Injection frequency • Cumulative number of weeks on treatment • Stratification group Baseline: Age 
 • Lesion size • GA presence • Smoking status • Genotype saliva sample status • Baseline BCVA (<=70/>70) • Baseline IRF • IRF • Baseline SRF • SRF • PED • SRF resolved (y/n) 	Treatment Visit Subject	Stratum Centre	Subject

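### The stratification factor is only an optional term in the primary BCVA model and the CRT model, at a small but avoidable cost in power

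*SAP*

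**What the plan says.** The design paragraph in SAP Section 1 allocates patients 1:1 "within the appropriate stratum depending on the treatment at baseline for the non-study eye". SAP 2.3 lists the strata again as a possible subgroup, the third being "one eye (first non-study eye) being treated with an anti-VEGF other than ranibizumab".

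In Table 2.8.2.5-1, "Stratification group" stands in the optional covariate column of MM_1 and MM_2 (BCVA) and MM_4 (CRT). The definite terms are treatment, baseline value, visit and their treatment-by-visit interaction, with subject as the random term. MM_2 to MM_4 carry "Stratum Centre" as optional class variables; that cell is blank in MM_1.

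The footnote formulas of shell Tables 14.2-2 (FAS), 14.2-3 (PPS) and 14.2-30 (CRT) have no stratum term. The FAS shell, headed "Random Effects Mixed Model", has no class-variable row, the PPS shell has one and the CRT shell has two. Both BCVA shells are marked as examples.

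SAP 2.8.2.2 says that "Statistical models with optional variables may be explored to identify which model(s) optimally fit the data" and that "the primary model will be fitted to the Per-Protocol Set as a supporting analysis". The non-inferiority rule in 2.8.2.5 names no numbered model.

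**The concern.** A factor used to stratify allocation normally belongs in the primary model. Stratification balances the arms on it. A model that omits it still counts the between-stratum variation as noise, so the standard error is too large for the estimator actually used.

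The primary model is also not stated outright. MM_1 and MM_2 have the same outcome and the same definite terms and differ only in optional ones. The definite set is probably what is meant: the BCVA shell formulas match it, and the sentence on exploring optional variables sits under supportive and sensitivity analyses. The SAP does not say so. At stake are a little power for the 5-letter decision and one pre-stated model for FAS and PPS.

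**Working it through.** **Inputs.** From SAP 2.12: margin 5 letters, SD 15, true difference 0, two-sided 95% limit (one-sided 0.025), 165 per group, 15% dropout. The share of variance explained by the stratum (R²) is not in the documents and is assumed to be 0 to 0.05. The value 0.10 is shown only for scale.

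**The plan's own figure.** n = 2 × 15² × (1.96 + 0.84)² / 5² gives 142 evaluable per arm (143 with the t distribution). Allowing for 15% dropout gives 168 or 169 by dividing by 0.85, and 164 or 165 by multiplying by 1.15. The stated 165 reproduces. In the other direction, 165 × 0.85 = 140 evaluable per arm: SE = 15 × √(2/140) = 1.793, and power = Φ(5/1.793 − 1.96) = 79.6%.

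**Effect of omitting the stratum, 140 per arm, 15 taken as the total SD.**
- Stratum in the model: power = Φ(5/(SE√(1−R²)) − 1.96).
- Stratum left out after stratified allocation: power = Φ((5/SE − 1.96)/√(1−R²)), and one-sided error = Φ(−1.96/√(1−R²)).

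| R² | Power with | Power without | Loss (points) | CI half-width with (3.51 without) | Error without |
|---|---|---|---|---|---|
| 0 | 79.6% | 79.6% | 0 | 3.51 | 2.50% |
| 0.01 | 80.0% | 79.8% | 0.3 | 3.50 | 2.44% |
| 0.02 | 80.4% | 79.9% | 0.6 | 3.48 | 2.39% |
| 0.05 | 81.6% | 80.2% | 1.4 | 3.43 | 2.22% |
| 0.10 | 83.6% | 80.9% | 2.8 | 3.33 | 1.94% |

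**With baseline BCVA in both models.** This is a simulation of the month-24 comparison, as an approximation to MM_1. It uses 200,000 trials per cell, allocation balanced within strata, assumed shares of 76/16/8%, and one common effect for the two treated-fellow-eye strata. Entries are power without v with the stratum:

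| Baseline BCVA R² (residual SD) | Stratum 0 | 0.02 | 0.05 | 0.10 |
|---|---|---|---|---|
| 0 (15.0) | 79.1 v 79.1 | 79.3 v 79.9 | 79.8 v 81.2 | 80.5 v 83.3 |
| 0.10 (14.2) | 83.3 v 83.3 | 83.5 v 84.0 | 83.8 v 85.1 | 84.5 v 86.9 |
| 0.20 (13.4) | 87.3 v 87.2 | 87.6 v 88.0 | 88.0 v 88.9 | 88.5 v 90.4 |

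Taken before rounding, the loss is 0.4 to 0.6 points at 2%, 1.0 to 1.4 at 5% and 1.9 to 2.8 at 10%. The upper limit lies about 0.03 letters too far out at 2% and 0.08 to 0.09 at 5%. At a true 5-letter deficit, false non-inferiority without the stratum is 2.5%, 2.4%, 2.1 to 2.2% and 1.9 to 2.0% across the four columns. With the stratum it is 2.4 to 2.6%.

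**What these R² values imply.** If 24% of patients have a treated fellow eye (assumed), the between-stratum difference is d = √R² × residual SD / √(0.24 × 0.76). That is 4.4 to 5.0 letters at 2%, 7.0 to 7.9 at 5% and 9.9 to 11.1 at 10%. The documents do not support the 10% case.

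**Dropout.** SAP 2.8.2.3 holds that the mixed model "is an appropriate model for data missing at random". If dropout depends on stratum and arm jointly, that assumption holds for this model only with the stratum in it. The check used generalised least squares over months 2, 12 and 24, with correlation 0.6, dropout after month 12, a stratum effect of 5 to 8 letters at all visits and 15% dropout among other patients (all assumed). Dropout of 10% v 20% by arm within the treated-fellow-eye patients shifts the difference by 0.03 to 0.04 letters without the term. Dropout of 5% v 35% shifts it by 0.08 to 0.13. With the term the shift is 0. If the stratum effect appears only at month 24, the shift at 10% v 20% is 0.11 to 0.17 without the term and 0.10 to 0.16 with it, so a main effect does not cure that case.

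**Coding.** Fitted as a single 1/2/3 slope, the stratum would capture 86% of the between-stratum variance for effects (0, d, d), 65% for (0, 0, d) and 23% for (0, d, 0), at the 76/16/8% shares.

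**The case against.** The strongest reply is that nothing of consequence follows. Omission is conservative, every non-zero loss rests on an assumed R², and zero loss is equally compatible with the documents. Stratum differences of 2 to 5 letters at a 24% share give R² of only 0.003 to 0.02, a loss of at most about 0.6 points. That stands, and it is why the point is minor.

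The signs that the term is unsettled are also thin. The class-variable column is evidently not exhaustive: MM_2 to MM_4 offer smoking status and other categorical covariates without listing them there. The single-slope risk is therefore speculative. The class-variable rows in the shells name no variable, and the FAS and PPS footnotes give the same formula. These details support the case for clarity and little else.

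Two practical objections concern the fix. Section 1 describes the first stratum as no fellow-eye treatment at baseline, whereas 2.3 and Listing 16.2.4-8 describe both eyes as treatment-naive. A fellow eye treated earlier but not at baseline fits only the former. In addition, the randomisation listing (16.1.7-1) has no stratum column. Using the stratum as randomised answers the first, and the SAP already treats that variable as available. MM_3 should be settled in the same edit, since it too lists the stratum as an optional class variable.

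None of this supplies a reason to leave the stratum optional.

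**Conclusion.** The concern holds as a minor one. Randomisation is stratified, the stratum is optional in MM_1, MM_2 and MM_4, the shell formulas omit it, and no supplied document makes it mandatory. The clinical study protocol cited in the SAP references was not supplied, so a rule there cannot be excluded.

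The cost is 0 to 1.4 points of power over an assumed stratum R² of 0 to 5%, in a design with about 79.6% power at 140 evaluable per arm before any covariate gain. No inflation of false non-inferiority is claimed. Bias is not claimed either, provided dropout does not depend jointly on stratum and arm. The gain from the fix is small, but it comes almost free and fixes one primary model in advance.

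**What to change.** - In Table 2.8.2.5-1, move the stratum to the definite fixed effects of MM_1, MM_2 and MM_4 for both FAS and PPS, and list it as a definite class variable in each. Specify the stratum as randomised, and reconcile the wording of the first stratum between Sections 1 and 2.3.
- Add the term to the formulas of shell Tables 14.2-2, 14.2-3 and 14.2-30, with identical class-variable rows in the FAS and PPS shells.
- State that the remaining optional terms are for sensitivity analyses only. In MM_1 the other one is accumulated treatment time, which is measured after randomisation.
- As a separate alignment, not a contradiction: Table 2.8.2.8-1 makes baseline BCVA optional in LR_2, LR_4, LR_10 and LR_11, while the matching shell footnotes include it. List it as mandatory in LR_2 and LR_4, and at post-baseline visits in LR_10 and LR_11. The shells already report only proportions at baseline.

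The cost is table and footnote edits and two degrees of freedom. The fellow-eye treatment categories are already collected (Listing 16.2.4-8); confirm that the stratum assigned at randomisation is held in the analysis data.
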